## Appendix A: Schedule of Assessments (continued)

Assessment:	Pre-randomization	Screening a (before randomization)	W1D1 (≤ 3 days after randomization)	Post-randomization								First Post-Treatment Follow-Up Visit (FU-1; 30+14 days after decision to discontinue study treatment) m	Second Follow-Up Visit (FU-2; 100±14 days after decision to discontinue study treatment) m			
				(± 3 Days)												
				W 3 D 1	W 4 D 1	W 6 D 1	W 7 D 1	W 9 D 1	W 10 D 1	W 12 D 1	W 14 D 1					
HRQOL- EQ-5D-5L i (Section 5.7.7)	≤ 14 days															
Health Care Resource Utilization (Section 5.7.8)																
Cabozantinib/placebo PK plasma samples j,k (Section 5.7.9)			X (prior to first dose)		X		X		X		X					
Nivolumab+ipilimumab PK serum samples k (Section 5.7.9)			X (prior to first dose)		X		X		X		X		X	X		
Immunogenicity blood sample k (Section 5.7.10)			X (prior to first dose)							X		W26D1	X	X		
Pharmacogenetic blood sample k (Section 5.7.11)			X (prior to first dose)													
Immune cell profiling blood sample k (Section 5.7.11)			X (prior to first dose)			X				X						
Plasma biomarker samples k (Section 5.7.11)			X (prior to first dose)		X		X		X		X		X			
Cell and/or pharmacogenomic blood sample k (Section 5.7.11)			X (prior to first dose)			X				X			X			
Concomitant medication (Section 7)				Document concomitant medication taken from 28 days before randomization through 30 days after the date of the decision to discontinue study treatment												

CONFIDENTIAL

Protocol XL184-313 Protocol Amendment 3.0

Page 153 of 193

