- Any SAEs assessed as related to study treatment or study procedures, even if the SAE occurs more than 100 days after the date of the decision to permanently discontinue study treatment.

Note: If the subject does not meet the eligibility criteria during screening, then SAEs only need to be reported from the time the subject signs the informed consent until the day when the subject has been determined to not be eligible for study participation.

SAEs that occur after the initial consent and through 100 days after the date of the decision to permanently discontinue study treatment must also be recorded on the CRF page.

The minimum information required for SAE reporting includes identity of investigator, site number, subject number, and an event description. Other important information requiring timely reporting are the SAE term(s), the reason why the event is considered to be serious (ie, the seriousness criteria), and the Investigator's assessment of the relationship of the event to study treatment. Additional SAE information including medications or other therapeutic measures used to treat the event, action taken with the study treatment because of the event, and the outcome/resolution of the event will be recorded on the SAE form.

In all cases, the Investigator should continue to monitor the clinical situation and report all material facts relating to the progression or outcome of the SAE. Furthermore, the Investigator may be required to provide supplementary information as requested by the Sponsor's Drug Safety personnel or designee.

When reporting SAEs, the following additional points will be noted:

- When the diagnosis of an SAE is known or suspected, the Investigator will report the diagnosis or syndrome as the primary SAE term, rather than as signs or symptoms. Signs and symptoms may then be described in the event description.
- Death will not be reported as an SAE, but as an outcome of a specific SAE, unless the event preceding the death is unknown. Terms of "Unexplained Death" or "Death from unknown origin" may be used when the cause is unknown. In these circumstances the cause of death must be investigated and the diagnosis amended when the etiology has been identified. If an autopsy was performed, the autopsy report should be provided.

CONFIDENTIAL

Protocol XL184-313 Protocol Amendment 3.0  
Page 119 of 193

- While most hospitalizations necessitate reporting of an SAE, hospitalizations that do not require SAE reporting are as follows:

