i HRQOL forms should be administered and collected prior to any other study-related activities for scheduled visits. Questionnaires should be completed prior to the clinic visit.

j For each on-treatment visit, the PK sample should be collected approximately 8 or more hours after the previous dose of cabozantinib/placebo, and if cabozantinib/placebo will be administered on that day, should be collected prior to cabozantinib/placebo administration. The investigator will ask the subject for the date and time of the most recent prior dose of cabozantinib/placebo and this information will be recorded on the appropriate CRF page.

k Central laboratory assessments are required for these measurements.

l An optional biopsy can be collected approximately 6 weeks after the first dose of study treatment.

m Date of the decision to permanently discontinue study treatment by the subject is defined as the later of the decision to permanently discontinue study treatment or the last dose of study treatment.

n In exceptional circumstances (eg, COVID-19 pandemic), alternative methods of distribution of oral treatment to subjects may be considered in accordance with the study site's local policies and all applicable regulations.

CONFIDENTIAL

Protocol XL184-313 Protocol Amendment 3.0  
Page 155 of 193

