## **Appendix H: Collection, Follow-Up, and Documentation Requirements for AEs, AESIs, and SAEs**

All AEs that are not serious and not AESIs (AEs of special interest; see [Table 8-1](#)) that start or worsen after the first dose of study treatment through the 30-day post-treatment follow-up (FU-1) visit are to be entered into the electronic CRF data capture system (EDC). Such events continuing at the FU-1 visit are to be documented as “ongoing” in the EDC and do not require further documentation for study purposes. These events do not require a Drug Safety SAE Form to be completed.

Additional requirements apply to the following events:

- All SAEs that are judged by the investigator to be not related to study treatment that start or worsen after the subject’s initial informed consent through the 100-day post-treatment follow-up (FU-2) visit are to have a Drug Safety SAE Form completed. Such events continuing at the FU-2 visit are to be documented as “ongoing” in the EDC and do not require further documentation for study purposes.
- All AEs leading to study treatment discontinuation that are judged by the Investigator to be related to study treatment and that are continuing at the FU-2 visit are to be followed by the Investigator until resolution, defined as fully resolved or  $\leq$  Grade 2 severity or the event is deemed stable/irreversible by the Investigator. In the EDC, only documentation of the status of “ongoing” at the FU-2 visit is required. If serious, the requirements for related SAEs apply.
- All AESIs (regardless of seriousness) that start or worsen after the subject’s initial informed consent through the FU-2 visit are to have a Drug Safety SAE Form completed and be entered into the EDC. Such events continuing at the FU-2 visit are to be followed until resolution (as defined above), with evidence of resolution provided on updates to the Drug Safety SAE Form. In the EDC, only documentation of the status of “ongoing” at the FU-2 visit is required.

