### **4.5.2. Extended Period**

To evaluate the incidence of adverse events of interest (AESIs) associated with study treatment, extended observation period is defined as the interval from the first dose date of study treatment to the earliest of the following:

- Date of last dose of last component of study treatment + 100 days, or
- Date of death, or
- Date subject withdrew consent for non-interventional study assessments, or
- Data cutoff date for analysis under consideration.

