## **6.4. Prior and Concomitant Immune Modulating Medications**

Immune-modulating medications (IMMs) are a select list of medications that were used to manage AEs due to study treatment. A list of the verbatim terms for these medications will be identified and provided along with the ATC and WHO-DD base substance preferred name. These will be summarized by treatment group in the Safety population by ATC and WHO-DD base substance preferred name. In addition, the following summaries will be provided:

- Subjects with prior use of IMMs
- Subjects with concomitant use of IMMs
- Subjects with concomitant use of IMMs for management of AEs
- Subjects with concomitant use of high dose corticosteroids for management of AEs where high dose is defined as  $\geq 40$  mg/day of prednisone or equivalent

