## 8.3. Adverse Events of Special Interest

Adverse events of special interest (AESIs) consist of AEs potentially associated with immune checkpoint inhibitor (ICI) therapies, cases of potential drug induced liver injury (DILI) and suspected transmission of an infectious agent by the study treatment.

Specific AEs may be observed due to treatment with ICIs. Routine and early recognition and management of these events may mitigate severe toxicities. Hence the sponsor has defined a set of preferred terms that are grouped under various AESI categories that will provide a consistent, reproducible, and transparent compilation of safety information over time. The select preferred terms are revisited and updated periodically.

Analysis of potential DILI is discussed in [Section 8.7.2](#) and cases of transmission of infectious agent by study treatment, if any, will be discussed in patient narratives.

The following summaries will be provided for potential adverse events associated with treatment due to ICI therapies for subjects in the Safety population. These summaries will be for such AESIs collected up to 100 days since last dose of study treatment:

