**Table 16: Adverse Event of Special Interest Summaries**

TEAE included	Row-levels (sorted by)	Columns
Subject Incidence by Group, Preferred Term and Severity		
All AESIs	AESI and PT (AESI, PT within AESI by descending frequency of Any Grade)	Worst severity: Any Grade, Grade 3-4, Grade 4, Grade 5
AESIs leading to dose reduction/delay: 
 
• Of at least one component
 
• Of all components due to the same AESI
 
• Oral components
 
• Of any infusion component
 
	AESI and PT (AESI, PT within AESI by descending frequency of Any Grade)	Worst severity: Any Grade, Grade 3-4, Grade 4, Grade 5
AESIs leading to discontinuation 
 
• Of at least one component
 
• Of all components due to the same AESI
 
• Oral components
 
• Of any infusion component
 
	AESI and PT (AESI, PT within AESI by descending frequency of Any Grade)	Worst severity: Any Grade, Grade 3-4, Grade 4, Grade 5
AESIs leading to initiation of immune-modulating medication	AESI and PT (AESI, PT within AESI by descending frequency of Grade 3-4)	Worst severity: Any Grade, Grade 3-4, Grade 4, Grade 5
AESIs leading to initiation of high dose (defined in Section 6.4 ) of immune-modulating medication	AESI and PT (AESI, PT within AESI by descending frequency of Grade 3-4)	Worst severity: Any Grade, Grade 3-4, Grade 4, Grade 5
AESIs leading to initiation of immune-modulating medication and any infusion treatment discontinuation	AESI and PT (AESI, PT within AESI by descending frequency Grade 3-4)	Worst severity: Any Grade, Grade 3-4, Grade 4, Grade 5
All serious AESIs	AESI and PT (AESI, PT within AESI by descending frequency of Any Grade)	Worst severity: Any Grade, Grade 3-4, Grade 4, Grade 5
Serious AESIs leading to initiation of immune-modulating medication	AESI and PT (AESI, PT within AESI by descending frequency of Grade 3-4)	Worst severity: Any Grade, Grade 3-4, Grade 4, Grade 5
Serious AESIs leading to initiation of high dose (defined in Section 6.4 ) of corticosteroids	AESI and PT (AESI, PT within AESI by descending frequency of Grade 3-4)	Worst severity: Any Grade, Grade 3-4, Grade 4, Grade 5
Time to Onset of Event		
AESIs	Time to first onset of AESIs by Group Term	Any Grade, Grade 3-5
AESIs leading to initiation of immune-modulating medication	Time to first onset of AESIs by Group Term	Any Grade, Grade 3-5

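### Medication recording stops 30 days after treatment ends, but SAP Table 16 classifies AESIs by immune-modulator use up to 100 days, so treated late AESIs may be under-counted

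*Protocol*

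**What the plan says.** **Medication recording.** The concomitant medication row of Protocol Appendix A reads: "Document concomitant medication taken from 28 days before randomization through 30 days after the date of the decision to discontinue study treatment". A footnote to the same schedule says that the decision date "is defined as the later of the decision to permanently discontinue study treatment or the last dose of study treatment". I take that definition to apply to the medication row too, so the 30 days start only when all study treatment has ended.

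**AESI collection.** Protocol Appendix H covers "All AESIs (regardless of seriousness) that start or worsen after the subject’s initial informed consent through the FU-2 visit" (about day 100). Each such event needs a Drug Safety SAE Form and an EDC entry. Protocol Section 8.3 sends every AESI, serious or not, through the SAE process. Under Section 8.2.1 the SAE form is to carry "Additional SAE information including medications or other therapeutic measures used to treat the event".

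**Analysis.** On AESIs linked to checkpoint inhibitors, SAP Section 8.3 says: "These summaries will be for such AESIs collected up to 100 days since last dose of study treatment". Among the Table 16 rows is "AESIs leading to initiation of immune-modulating medication", with parallel rows for high-dose use. SAP Section 6.4 identifies these drugs from verbatim medication terms coded to ATC and WHO-DD. It also plans a count of "Subjects with concomitant use of high dose corticosteroids for management of AEs where high dose is defined as" 40 mg/day or more of prednisone or equivalent. It names no source form and no time window.

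**The concern.** To place an AESI in a treated row, the analyst needs a record that an immune modulator was started for it and, for the high-dose rows, at what daily dose. The coded medication data are the natural source, and the only one that SAP Section 6.4 hints at. The protocol schedules no entry there after day 30. If Table 16 is programmed from those data alone, an AESI first treated between day 31 and day 100 counts as an AESI but drops out of the treated subset. The incidence rows would be too low. The time-to-onset and time-to-resolution rows would lose their latest events, so onset of treated immune events would look earlier than it was.

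These rows describe how much immune toxicity needed steroids or other immune suppression, which is a main safety question for a regimen that adds a third agent to two checkpoint inhibitors. Protocol Section 8.3.1 itself expects some immune events to start late.

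**Working it through.** The plan gives no figure to reproduce. The check compares windows and then goes through the Table 16 rows.

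**1. Length of the gap.** Let L be the last dose of the last component and d the days from L to the discontinuation decision (d = 0 if the decision comes first).
- Medication record ends at L + d + 30 (Appendix A with its footnote).
- AESI summary ends at L + 100 (SAP 4.5.2 and 8.3), or earlier on death, withdrawal of consent for non-interventional assessments, or data cutoff.
- Uncovered days = 100 − (d + 30) = 70 − d, if positive.

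With d = 0 this is 70 of 100 post-treatment days. It shrinks as the decision lags the last dose. After an 84-day hold, the 12-week limit in Protocol 3.6.1, there is no gap. Seventy days is therefore a maximum.

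**2. Do the SAP's definitions close it?** SAP 4.6 runs concomitant therapy to the end of the safety observation period without saying whether that is the 30-day standard or the 100-day extended period. Even on the 100-day reading, Appendix A schedules no medication record after day 30 to fill it.

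**3. Does the SAE form close it?** The form should name the treating drug for any AESI through FU-2. Neither document says that its contents feed Table 16 or are coded with the medication data. Nor does either say that it records the daily dose needed for the 40 mg/day threshold.

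**4. Which rows are exposed?**

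| Table 16 block | Rows using immune modulators or high-dose steroids | Exposed? |
|---|---|---|
| Incidence, all AESIs | 2 | Yes |
| Incidence, serious AESIs | 2 | Yes |
| Incidence, with infusion discontinuation | 1 | Hardly |
| Time to onset | 2 | Yes |
| Time to resolution | 2 | Yes |
| Recurrence after rechallenge | 2 | No |

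The total is 2 + 2 + 1 + 2 + 2 + 2 = 11 rows, of which 2 + 2 + 2 + 2 = 8 are exposed. Rechallenge requires further dosing, which cannot follow permanent discontinuation of everything. An AESI that starts after day 30 cannot have stopped an infusion already stopped. The infusion-discontinuation row could miss only an AESI that caused the stop and was first treated more than 30 days after all treatment ended.

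**5. Timing against the early-risk period.** Protocol 8.3.1 says that most immune-related events fall in the first 12 weeks of exposure (days 1 to 84). For a subject who stops all treatment on an induction dosing day, with d = 0:

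| Stop | Medication record to | AESI summary to | Days 1–84 uncovered |
|---|---|---|---|
| W1D1 (day 1) | day 31 | day 101 | 84 − 31 = 53 (63%) |
| W4D1 (day 22) | day 52 | day 122 | 84 − 52 = 32 (38%) |
| W7D1 (day 43) | day 73 | day 143 | 84 − 73 = 11 (13%) |
| W10D1 (day 64) | day 94 | day 164 | 0 |

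The loss within the early-risk period is substantial only for very early stopping of all components.

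**The case against.** The strongest reply is that the information is collected. Every AESI through FU-2 has an SAE form, the form records treatment, and it is updated until resolution. SAP 6.4 names no form, so its silence does not exclude this one. The CRF completion guidelines, which are not among the documents, may also ask for treatment of late AESIs. This stands as far as it goes. A reader might infer that late immune events will appear untreated in the report. The documents do not support that: it would follow only if the SAE forms were ignored. What remains is that the link is not stated and that dose capture is not assured.

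Three further points stand.
- The gap needs all study treatment to have ended. Protocol 3.6.1 allows one component to continue, and a subject who stops the infusions but stays on the oral drug is still inside medication recording.
- The all-AESI and all-serious-AESI rows still run to day 100, so total immune toxicity is not hidden.
- These are descriptive tables with no formal comparison between arms (Protocol 9.4, SAP 8). No endpoint, test or stopping rule is touched.

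A reader might also infer that the under-count favours the experimental arm. That requires earlier complete stopping in that arm. The protocol assumes earlier progression in controls (median PFS 11.6 against 17.6 months), which could push the other way. The direction is unknown.

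**Conclusion.** The mismatch is real and unreconciled. Following the stated collection rule and building Table 16 from coded medication data could under-count treated late AESIs in about eight rows. The rechallenge rows are not affected, and the row combining immune modulators with infusion discontinuation hardly is.

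The gap is at most 70 days per subject, after all study treatment has ended. That is a share of calendar time and should not be read as a share of events, most of which the protocol expects early. If a fraction f of treated AESIs first receive the drug after the medication window closes, and none is recovered from the SAE forms, each incidence row is low by f. The documents give no value for f, and any assumed percentage would simply reappear as the answer.

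The conclusion assumes that no unseen CRF instruction already extends recording of AESI treatment, and that the footnote's decision date governs the medication row. It is a safety-reporting defect worth correcting and has no bearing on the efficacy conclusions.

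**What to change.** **Protocol Appendix A:** extend recording of corticosteroids and other immune modulators given for an AESI through FU-2, with drug, dose and dates. This changes what is recorded and leaves treatment untouched.

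**SAP 6.4 and 8.3:** state that the immune-modulator and high-dose rows of Table 16 use the extended (100-day) period, name the data source, and require reconciliation with the Drug Safety SAE forms.

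**Data already collected:** populate the treatment flag for late AESIs from the SAE forms where drug and dose are given. Otherwise restrict these rows to AESIs with onset by day 30 and label them so. The label should add that medication recording ended at day 30, because an AESI that starts just before then may first be treated afterwards.

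**Cost:** a CRF completion instruction for one group of drugs at a visit that already takes place, some extra data entry, and reconciliation against forms already held. No endpoint, alpha or sample size changes.

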## Appendix A: Schedule of Assessments (continued)

Assessment:	Pre-randomization	Screening a (before randomization)	Post-randomization										First Post-Treatment Follow-Up Visit (FU-1; 30±14 days after decision to discontinue study treatment) m	Second Follow-Up Visit (FU-2; 100±14 days after decision to discontinue study treatment) m			
			( $\pm$ 3 Days)														
			W 3 D 1	W 4 D 1	W 6 D 1	W 7 D 1	W 9 D 1	W 10 D 1	W 12 D 1	W 14 D 1							
Adverse events (Section 8)			Document new or worsening AEs from informed consent for SAEs and from first dose for nonserious AEs. Continue monitoring through 30 days (100 days for unrelated SAEs [Table 8-1]) after the date of the decision to permanently discontinue study treatment. AE information will be collected at study visits and may also be collected at any time over the phone or by spontaneous subject report. On W1D1 AEs will be documented pre- and post-dose. Related AEs leading to study treatment discontinuation, AESIs (regardless of causality), and related SAEs are to be followed until resolution, $\leq$ Grade 2 severity, or determination by the Investigator that the event is stable or irreversible (see Section 8.3).														
Cabozantinib / Placebo dosing (Section 6.1.1.1 / 6.1.1.2)			Cabozantinib or placebo tablets given on W1D1 after nivolumab/ipilimumab infusion. Taken once daily at home thereafter until study treatment is discontinued.														
Nivolumab dosing (Section 6.1.1.3; weight-based dose W1D1, W4D1, W7D1, W10D1, flat dose from W14D1 onwards)		X		X		X		X			Nivolumab will be administered as an IV infusion at the clinic W14D1 and every 4 weeks until treatment is discontinued (to a maximum of 2 years).						
Ipilimumab dosing (Section 6.1.1.3; weight-based dose W1D1, W4D1, W7D1, W10D1)		X		X		X		X			No further doses						
Dispense/return of oral study drug and compliance accounting (Section 6.5) b		X		X		X		X		X	Every 4 weeks (W18D1, W22D1 etc)						
Additional systemic anti-cancer treatment and survival status (Sections 5.7.12)			All treated subjects will be contacted at each post-treatment visit, including FU-1, FU-2, and every 12 weeks (+ 14 days) after FU-2 visit until death. Any subjects who are randomized but not treated will be contacted every 12 weeks post-randomization until death.														

a Results of screening assessments must be reviewed before randomization to confirm that the subject meets the eligibility criteria.

b Informed consent may be obtained greater than 28 days prior to randomization but must be provided before any study-specific procedures are performed; however, evaluations performed as part of routine care prior to informed consent can be utilized as screening evaluations if permitted by the site's IRB/EC policies.

c Additional ECGs should be performed if clinically indicated.

CONFIDENTIAL

Protocol XL184-313 Protocol Amendment 3.0

Page 154 of 193

d This assessment is intended to confirm suitability for treatment after randomization. If this assessment has been performed during screening within 14 days (7 days for pregnancy test for females of child-bearing potential) prior to first dose (W1D1), this assessment does not need to be performed on W1D1 unless the subject's clinical status has changed (eg, onset of new symptoms indicative of clinical deterioration). If the assessment is performed on W1D1, the results must be available to and reviewed by the Investigator prior to any treatment being administered.

e Serum chemistry, hematology, and urinalysis laboratory samples must be collected within 72 hours and the results be reviewed before any study treatment infusion administered on study. These assessments are not required prior to the first dose if there has been no change in subject's clinical status since screening. Results (with the exception of routine urinalyses and pregnancy tests) must be provided to the local laboratory management vendor. See [Section 5.7.5](#) and the Laboratory Manual for more detailed information on laboratory assessments.

f For women under the age of 55 years, confirm menopause as needed.

g Hepatitis B surface antigen and Hepatitis C antibody (with reflex testing of HCV RNA if antibody test is positive) to be assessed at screening.

h Shipment of archival tumor tissue (unstained slides or paraffin block) to the study central laboratory prior to randomization. The tissue can be obtained/sampled from any organ except brain or bone and must be biopsied no more than 2 years prior to the date of informed consent. Alternatively, a fresh tumor sample must be obtained and shipped to the study central laboratory prior to randomization if archival tissue is unavailable or inadequate.

i HRQOL forms should be administered and collected prior to any other study-related activities for scheduled visits. Questionnaires should be completed prior to the clinic visit.

j For each on-treatment visit, the PK sample should be collected approximately 8 or more hours after the previous dose of cabozantinib/placebo, and if cabozantinib/placebo will be administered on that day, should be collected prior to cabozantinib/placebo administration. The investigator will ask the subject for the date and time of the most recent prior dose of cabozantinib/placebo and this information will be recorded on the appropriate CRF page.

k Central laboratory assessments are required for these measurements.

l An optional biopsy can be collected approximately 6 weeks after the first dose of study treatment.

m Date of the decision to permanently discontinue study treatment by the subject is defined as the later of the decision to permanently discontinue study treatment or the last dose of study treatment.

n In exceptional circumstances (eg, COVID-19 pandemic), alternative methods of distribution of oral treatment to subjects may be considered in accordance with the study site's local policies and all applicable regulations.

CONFIDENTIAL

Protocol XL184-313 Protocol Amendment 3.0  
Page 155 of 193

